HIV Prevention Trials Network PROTOCOL CLARIFICATION MEMORANDUM #1

HIVNET/HPTN 055: HIV Prevention Preparedness Study Version 1.0, 12 August 2002

21 January 2004

Summary of Clarification

Section 3.3, Paragraph 2: text is modified to clarify and reconcile procedures outlined in the protocol, with the Study-Specific Procedures Manual (SSP), Visit Checklists, and site-specific Standard Operation Procedures (SOPs) regarding the relative timing of assigning the Participant ID number and obtaining informed consent for screening.

Implementation

The protocol clarification detailed in this memorandum should be implemented immediately. This clarification does not result in a change in the informed consent being used in the study. If The HPTN 055 protocol is amended in the future, this clarification will be incorporated into the next version.

The HPTU will submit HPTN 055 Protocol Clarification Memorandum #1 to all responsible Institutional Review Boards (IRBs) for informational purposes. IRB approval of HPTN 055 Protocol Clarification Memorandum #1 is not required.

The following protocol modifications, indicated by strikethrough or under-score text, made to the HPTN 055 Protocol:

Section 3.3, Paragraph 2:

During screening, potential participants will be assigned an ID number. After providing written informed consent for screening, potential study participants will be assigned an ID number and asked to provide demographic information, behavioral eligibility information, and locator information.

DATE: 26 February 2003

RE: LETTER OF AMENDMENT FOR: HIVNET/HPTN 055, HIV Prevention

Preparedness Study, Version 1.0, dated 12 August 2002.

TO: HPTN 055 Investigators of Record

CC: HPTN 055 Protocol Team

FROM: [name], HPTN CORE Protocol Specialist

THE FOLLOWING INFORMATION IMPACTS THE HIVNET/HPTN 055 STUDY AND MUST BE FORWARDED TO YOUR INSTITUTIONAL REVIEW BOARDS (IRBS) AND/OR ETHICS COMMITTEES (ECS) AS SOON AS POSSIBLE FOR THEIR INFORMATION AND REVIEW. IT MUST BE APPROVED BEFORE IMPLEMENTATION.

THE FOLLOWING INFORMATION MAY ALSO IMPACT THE HIVNET/HPTN 055 SAMPLE INFORMED CONSENT FORMS. YOUR IRB/EC WILL BE RESPONSIBLE FOR DETERMINING THE PROCESS OF INFORMING SUBJECTS OF THE CONTENTS OF THIS LETTER OF AMENDMENT.

PLEASE FILE THIS LETTER AND ANY IRB CORRESPONDENCE IN YOUR REGULATORY FILE AND OTHER PERTINENT FILES. YOU ARE NOT REQUIRED TO SUBMIT THESE DOCUMENTS TO THE PROTOCOL REGISTRATION OFFICE UNLESS THE CHANGES RESULT IN A CHANGE TO THE INFORMED CONSENT FOR YOUR SITE.

Summary of Revisions

- The listing of study sites throughout the protocol is updated to not include Chililabombwe, Zambia.
- The protocol is clarified throughout to specify that chlamydia and gonorrhea testing will be performed
 by standard diagnostic methods in use at each study site, rather than by ligase chain reaction (LCR).
 Standard diagnostic methods to test for chlamydia and gonorrhea currently in use at each site are
 summarized in the following table:

Site	Chlamydia Test	Gonorrhea Test
Duban, South Africa	SDA	SDA
Hlabisa, South Africa	SDA	SDA
Lusaka, Zambia	ELISA	Culture
Moshi, Tanzania	ELISA	Culture

ELISA, Enzyme-linked Immunosorbent Assay; SDA, Strand Displacement Amplification

- The number of infections listed in Tables 1 and 2 of the protocol's statistical section is corrected.
- The Protocol Team Roster is updated.

Upon receipt of IRB/EC approval, the following protocol modifications, indicated by strikethrough and underscored text, will be implemented:

1. In the List of Abbreviations and Acronyms:

LCR ligase chain reaction

2. In the Protocol Team Roster:

[name], MS HPTN CORE Protocol Specialist (back-up)

[name]
HPTN CORE Protocol Specialist
Family Health International
[name]
[name]
[contact]
T: [contact] [name]

3. In the Schema:

Chililabombwe, Zambia

F: [contact]

4. In the Schema:

1200 participants total (240 participants per site).

5. In Section 2.2:

The is a prospective cohort study to be conducted at HPTN study sites located in Chililabombwe Zambia; Durban, South Africa; Hlabsia South Africa; Lusaka, Zambia; and Moshi, Tanzania.

- 6. In Section 4.2.2, add bullet:
 - Specimen collection for chlamydia and gonorrhea testing (by standard local method).
- 7. In Section 4.2.3, second bullet:
 - Urine ligase chain reaction (LCR) Chlamydia and gonorrhea testing by standard local method.
- 8. In Section 4.3.2, add bullet:
 - Specimen collection for chlamydia and gonorrhea testing (by standard local method).
- 9. In Section 4.3.3, second bullet:
 - Urine LCR Chlamydia and gonorrhea testing by standard local method if clinically indicated.

- 10. In Section 4.4.2, add bullet:
 - Specimen collection for chlamydia and gonorrhea testing (by standard local method):
 - Quarterly.
 - Additionally when clinically indicated.
- 11. In Section 4.4.3, second bullet:
 - Urine LCR Chlamydia and gonorrhea testing by standard local method:
- 12. In Section 6.3, Tables 1 and 2:

Table 1
95% Exact Confidence Intervals for Infection Rates
Observed in a Six-Month Follow-up Period

. Infections Observed	Observed Infection Rate	95% Exact Confidence Interval
 12	1.7%	0.2-6.2%
24	3.4%	0.9-8.8%
 36	5.1%	1.8-11.2%
4 8	6.8%	2.9-13.5%
5 10	8.5%	4.0-15.7%
6 12	10.3%	5.3-17.9%

Table 2
95% Exact Confidence Intervals for Infection Rates
Observed in a Twelve-Month Follow-up Period

. Infections Observed	Observed Infection Rate	95% Exact Confidence Interval
24	1.7%	0.4-4.4%
4 8	3.4%	1.4-6.7%
6 12	5.1%	2.6-9.0%
816	6.8%	3.9-11.1%
10 20	8.5%	5.2-13.2%
1224	10.3%	6.5-15.3%

- 13. In Section 8.1, fourth bullet:
 - Urine for pregnancy testing, ehlamydia and gonorrhea LCR, dipstick urinalysis, and culture.
- 14. In Section 8.1, add seventh bullet:
 - Specimen for chlamydia and gonorrhea testing by standard local method (type of specimen dependent on local test).
- 15. In Appendix I, Schedule of Study Visits and Procedures:

urine LCR for chlamydia and gonorrhea testing by standard local method

A Study of the HIV Prevention Trials Network

Sponsored by:

Division of AIDS, US National Institute of Allergy and Infectious Diseases
US National Institute of Child Health and Human Development
US National Institute of Mental Health
US National Institute on Drug Abuse
US National Institutes of Health

Protocol Chairs:

[name], MPH, ScD Harvard School of Public Health

[name] South Africa Medical Research Council

[name] University of Miami School of Medicine

> FINAL Version 1.0 12 August 2002

TABLE OF CONTENTS

		BBREVIATIONS AND ACRONYMS	
		L TEAM ROSTER	
SCH	HEMA .		6
1	INTE	RODUCTION	7
•	1.1	Background	
	1.2	Rationale	
2	STU	DY OBJECTIVES AND DESIGN	9
	2.1	Objectives	
	2.2	Study Design	
3	STU	DY POPULATION	12
	3.1	Inclusion Criteria	12
	3.2	Exclusion Criteria	13
	3.3	Screening and Enrollment Process	14
	3.4	Co-Enrollment Guidelines	15
	3.5	Participant Retention	16
	3.6	Participant Withdrawal	17
4	STU	DY PROCEDURES	17
	4.1	Pre-Screening	17
	4.2	Screening Visit	17
	4.3	Enrollment Visit	18
	4.4	Follow-up Visits	19
	4.5	Interim Contacts and Visits	22
	4.6	Final Contact	23

Family Health International [name] [contact] T: [contact] F: [contact]

[name] Co-Investigator

Medical Research Council [name] [contact] T: [name] F: [name]

[name] HPTN Central Lab Co-Investigator

Magee Womens Hospital Department of OB/GYN [name] [contact] T: [contact] F: [contact]

[name], MPH, ScD

Protocol Co-Chair

Harvard School of Public Health [name] [contact]

T: [contact] F: [contact]

[name], MS

HPTN SDMC Statistical Research Associate

FHCRC—SCHARP [name] [contact] T: [contact] F: [contact]

[name], MHS HPTN SDMC Protocol Operations Coordinator

FHCRC—SCHARP [name] [contact] T: [contact] F: [contact]

[name] HPTN SDMC Protocol Statistician

FHCRC—SCHARP [name] [contact] T: [contact] F: [contact]

PROTOCOL TEAM ROSTER (continued)

[name] **Protocol Co-Chair**

Medical Research Council [name] [contact] T: [name] F: [name]

[name], DSc, MPH

Co-Investigator

Harvard School of Public Health [name] [contact] T: [contact] F: [contact]

[name] [name] **NIAID Medical Officer**

Division of AIDS/NIAID/NIH [name] [contact] T: [contact] F: [contact]

[name], PhD

University of Alabama, Birmingham [name] [contact] T: [contact]

F: [contact]

[name] **Protocol Co-Chair**

University of Miami School of Medicine [name] [contact]

T: [contact] F: [contact]

SCHEMA

Purpose: To prepare for implementation of HPTN 035, A Phase II/III Safety and

Effectiveness Study of the Vaginal Microbicides BufferGel and PRO 2000/5

Gel (P) for the Prevention of HIV Infection in Women.

Design: Prospective cohort study with a six-month accrual period and 6-12 months of

follow-up for each enrolled participant.

Study Population: Sexually active HIV-uninfected women from the study sites listed below.

Study Size: 1200 participants total (240 per site).

Study Duration: Accrual will require six months. Each participant will be maintained in

follow-up for a minimum of six months and a maximum of 12 months. At each site, the duration of follow-up will depend on the timing of initiation of

HPTN 035.

Primary Objective:

• To estimate rates of HIV seroincidence among women targeted for inclusion in HPTN 035.

Secondary Objectives:

- To develop and describe the accrual process and estimate rates of accrual into a standardized HIVrelated research study among women targeted for inclusion in HPTN 035.
- To estimate rates of retention in a standardized HIV-related research study among women targeted for inclusion in HPTN 035.
- To describe the demographic characteristics and HIV risk behaviors of women targeted for inclusion in HPTN 035.
- To estimate prevalence and incidence rates of the following among women targeted for inclusion in HPTN 035:
- Pelvic exam findings involving deep epithelial disruption
- Genital ulcer disease
- Other genital signs and symptoms
- Bacterial vaginosis
- Candidiasis
 - **Study Sites:**
 - Chililabombwe, Zambia
 - Durban, South Africa
 - Hlabisa, South Africa
 - Moshi, Tanzania
 - Lusaka, Zambia

- Chlamydia infection
- Gonorrhea infection
- Syphilis infection
- Trichomoniasis

1 INTRODUCTION

1.1 Background

HIV/AIDS continues to exact a devastating toll on the health, economic and political infrastructure, and social fabric of communities worldwide. The Joint United Nations Programme on HIV/AIDS (UNAIDS) estimates that 40 million adults and children were living with HIV/AIDS at the end of 2001, and that about 14,000 new infections are occurring each day. Over 95 percent of new infections are occurring in developing countries where there is little access to the treatments that have prolonged life in industrialized countries.

It has been stated that a safe and effective vaccine remains the best hope for ending the HIV/AIDS pandemic, however the timeline for developing and making available a safe and effective HIV/AIDS vaccine to communities affected by the pandemic remains unclear. While the search for an HIV/AIDS vaccine continues, additional research must be conducted to develop and test non-vaccine strategies to prevent the spread of HIV.

The United States (US) National Institutes of Health (NIH) established the HIV Prevention Trials Network (HPTN) for this purpose. This global network is the NIH's largest multicenter research network dedicated to HIV prevention, and is comprised of a Coordinating and Operations Center (CORE), a Statistical and Data Management Center (SDMC), a Central Laboratory, and 26 research sites and sub-sites located in Africa, Asia, Eastern Europe, South America, and the US. The HPTN focuses on six areas of HIV prevention research, as follows:

- Interventions to prevent mother-to infant HIV transmission.
- Interventions termed microbicides designed for vaginal and/or rectal use to prevent sexual transmission of HIV.
- Interventions to reduce behaviors that expose people to HIV.
- Interventions to prevent HIV infection through the reduction of injection drug use.
- Interventions to control other sexually transmitted diseases and thereby reduce the risk of HIV infection.
- Interventions based on antiretroviral therapy to prevent transmission and acquisition of HIV.

The HPTN conducts research in these six areas at all phases of development, ranging from pilot/feasibility studies to Phase I and II safety studies to Phase III efficacy and effectiveness studies. While early phase studies of a particular intervention are underway, work will proceed in parallel to ensure network-wide planning and preparedness to conduct Phase III studies of interventions shown to be safe and acceptable in earlier phase studies. For example, HPTN 035, A Phase II/III Safety and Effectiveness Study of the Vaginal Microbicides BufferGel and PRO 2000/5 Gel (P) for the Prevention of HIV Infection in Women, has been developed to determine the effectiveness of two candidate vaginal microbicides that have been shown in Phase I studies to be safe and well tolerated when applied intravaginally as well as topically to the penis.

1.2 Rationale

Previous prevention trial planning efforts have indicated that Phase III studies of HIV prevention interventions will require the participation of large numbers — from several hundred to several thousand — of persons at high risk for HIV infection. In addition to accruing large numbers of participants, research centers conducting Phase III HIV prevention studies must retain participants in extended periods of follow-up — from several months to several years — in order to preserve the statistical power of the study as well as avoid potentially biased results that may not accurately reflect the impact of the intervention in the target population.

The design of Phase III HIV prevention trials to be conducted in the HPTN will depend on the efficacy or effectiveness of the intervention being studied as well as the interplay of the four parameters referenced above: the number of participants enrolled, the HIV incidence rate among enrollees, the duration of follow-up, and the number of participants retained in follow-up. The potential impact of these parameters is illustrated in the tables below, which present the number of study participants required to adequately power a two-arm placebo-controlled phase III HIV prevention study assuming various levels of intervention efficacy (E), annual HIV incidence rates (I), durations of participant follow-up (D), and semiannual retention rates (R).

						R=95%				
			I=2%			I=5%			I=8%	
		D=12	D=18	D=24	D=12	D=18	D=24	D=12	D=18	D=24
E=25%	S=515	31,039	21,330	16,472	12,578	8698	6758	7964	5541	4331
E=50%	S=95	6645	4564	3523	2689	1857	1441	1700	1181	921
E=75%	S=29	2459	1689	1303	994	686	532	628	436	339
E=90%	S=16	1503	1032	796	607	419	325	383	266	207

Notes: S=number of seroconversions observed. Power=90%, Type I error=5%.

						R=85%				
			I=2%			I=5%			I=8%	
		D=12	D=18	D=24	D=12	D=18	D=24	D=12	D=18	D=24
E=25%	S=515	34,604	25,020	20,287	14,016	10,191	8307	8869	6485	5314
E=50%	S=95	7408	5354	4340	2996	2177	1772	1894	1382	1131
E=75%	S=29	2742	1981	1605	1108	804	654	700	510	417
E=90%	S=16	1675	1210	981	677	491	400	427	311	254

Notes: S=number of seroconversions observed. Power=90%, Type I error=5%.

As indicated above, dramatically different study designs may be required depending on the ability of HPTN research centers to recruit study participants and the rate of HIV incidence observed in study populations. As such, in order to realistically plan for future Phase III studies, information must be obtained to characterize these parameters at HPTN sites. HPTN sites also must develop strategies to achieve high rates of participant retention throughout the duration of a prospective study.

HPTN 035 has been designed to determine whether either of two candidate vaginal microbicides — BufferGel and PRO 2000/5 Gel (P) — are at least 33 percent effective in preventing HIV infection. In order to determine effectiveness within a period a three years, HPTN 035 requires accrual of over 8000 women at high risk for HIV infection within 23 months. The study also requires high rates of participant retention for 12-24 months of follow-up and an average HIV seroincidence rate of 5-6 percent among enrolled participants.

Building on prior NIH-sponsored and other work, several of the HPTN sites designated to conduct HPTN 035 have established effective standard operating procedures to recruit and retain high risk populations in research studies, and have characterized HIV incidence rates in these populations. Work is now required to establish a similar research infrastructure and knowledge base at HPTN sites not previously represented in HIV prevention research networks. This HIV Prevention Preparedness Study serves that purpose.

2 STUDY OBJECTIVES AND DESIGN

2.1 Objectives

2.1.1 Primary Objective

The primary objective of this study is to estimate rates of HIV seroincidence among women targeted for inclusion in HPTN 035.

2.1.2 Secondary Objectives

The secondary objectives of this study are to:

- Develop and describe the accrual process and estimate rates of accrual into a standardized HIV-related research study among women targeted for inclusion in HPTN 035.
- Estimate rates of retention in a standardized HIV-related research study among women targeted for inclusion in HPTN 035.
- Describe the demographic characteristics and HIV risk behaviors of women targeted for inclusion in HPTN 035.
- Estimate prevalence and incidence rates of the following among women targeted for inclusion in HPTN 035:
 - Pelvic exam findings involving deep epithelial disruption
 - Genital ulcer disease
 - Other genital signs and symptoms
 - Bacterial vaginosis (BV)
 - Candidiasis
 - Chlamydia infection
 - Gonorrhea infection
 - Syphilis infection
 - Trichomoniasis

2.2 Study Design

This is a prospective cohort study to be conducted at HPTN study sites located in Chililabombwe, Zambia; Durban, South Africa; Hlabisa, South Africa; Lusaka, Zambia; and Moshi, Tanzania. The study design and visit/procedures schedule are summarized in the Schema and in Appendix I. All procedures are consistent with those specified for implementation in HPTN 035.

Each study site will target enrollment of 240 study participants over the course of a six-month accrual period, according to the following schedule of monthly enrollment targets:

- Study month 1: 20 participants
- Study month 2: 30 participants
- Study month 3: 40 participants
- Study month 4: 50 participants
- Study month 5: 50 participants
- Study month 6: 50 participants

The study follow-up period then will extend for at least six months, and up to a maximum of 12 months, from the end of the accrual period.

It is expected that each study site will be activated to implement HPTN 035 by the end of the six-month follow-up period, however if this is not the case, the follow-up period may be extended for up to another six months, pending activation of HPTN 035. Possible reasons for a delay in activation of HPTN 035 include delays in finalizing the HPTN 035 protocol and implementation plans, delays in manufacturing and packaging the investigational products for HPTN 035, delays in obtaining ethical review and approval of the HPTN 035 protocol, and indication based on performance in this study that additional preparedness work is required prior to transitioning to HPTN 035. On a site-by-site basis, upon activation of HPTN 035, this study will be terminated and participants will be invited to screen for HPTN 035.

As described more fully in Section 3.3, potential study participants will be screened for eligibility and enrolled in the study over the course of up to 30 days, and over the course of at least one Screening Visit and one Enrollment Visit.

Enrolled participants then will complete monthly follow-up assessments throughout the duration of their participation. At each visit, participants will complete an interval medical/menstrual history and undergo pregnancy testing. HIV and sexually transmitted disease (STD) risk reduction counseling messages will be reinforced as needed and condoms and other prevention supplies will be distributed.

Each quarter, participants additionally will undergo a structured interview to ascertain HIV risk behaviors and receive HIV/STD pre-test, risk reduction, and post-test counseling. Participants also will undergo pelvic exams with wet mount testing for BV, candidiasis, and trichomoniasis; colposcopic evaluations will be performed at selected sites in accordance with the CONRAD/WHO Manual for the Standardization of Colposcopy for the Evaluation of Vaginal Products, Update 2000. For participants found to have a genital ulcer on pelvic exam, the ulcer will be swabbed for multiplex polymerase chain reaction (PCR) testing at the HPTN Central Lab for chancroid, herpes simplex virus 2 (HSV-2), and syphilis. Follow-up testing for chlamydia, gonorrhea, syphilis, and HIV (see Appendix II) will be performed quarterly, and additionally if clinically indicated. A sample of HIV test results will be confirmed for quality assurance purposes by the HPTN Central Laboratory.

Monthly visits other than those in which pelvic exams are scheduled may take place either on-site, in a participant's home, or at other community-based locations, depending on site capacities and site and participant preferences. If genital symptoms are reported during an off-site visit, the participant will be instructed to report to the on-site clinic as soon as possible for a pelvic exam. Other participant-initiated interim visits may occur at any time during follow-up, for example to obtain additional HIV counseling and testing.

All HIV and STD testing will be performed in the context of pre-test, risk reduction and post-test counseling. Study sites will provide this counseling in accordance with locally-accepted standards of practice and will document their counseling policies and procedures prior to study implementation for purposes of staff training, quality assurance, and study monitoring. In accordance with NIH policies, study participants must receive their HIV test results in order to remain eligible for study participation.

Participants who are found to have an STD or other reproductive tract infection will be provided counseling, treatment, and follow-up care in accordance with World Health Organization (WHO) guidelines, free-of-charge. Such participants will be encouraged to refer their partners for STD diagnosis and treatment if applicable. Participants who become pregnant during the study will be maintained in follow-up until the initiation of HPTN 035, as will participants who become infected with HIV. Participants who become infected with HIV will be counseled and referred to available sources of medical and psychosocial care and support, as well as to any available research studies for HIV-infected persons.

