6 STATISTICAL CONSIDERATIONS

6.1 Review of Study Design

This is a prospective cohort study. Accrual of 240 participants at each participating study site will be completed over the course of six months. Each participant will complete a minimum of six and a maximum of 12 scheduled monthly follow-up assessments. The total length of the study will be 12-18 months.

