6.2.1 Secondary Endpoints

Consistent with the secondary study objectives, the following will be assessed as secondary endpoints:

- Potential participants screened for the study, and the screening outcome for each screenee.
- Participants enrolled in the study.

- Participants retained in the study until the site-specific study end date.
- Demographic characteristics of women screened for and/or enrolled in the study, including:
 - Age
 - Race/ethnicity
 - Educational level
 - Employment status
 - Income level
- HIV risk behaviors reported by women enrolled in the study, including:
 - Number of sex partners
 - Frequency of vaginal intercourse
 - Frequency of unprotected vaginal intercourse
 - Frequency of anal intercourse
 - Frequency of unprotected anal intercourse
- Prevalent (i.e., at screening/enrollment) and incident (i.e., during follow-up) occurrences of the following:
 - Pelvic exam findings involving deep epithelial disruption
 - Genital ulcer disease
 - Other genital signs and symptoms
 - Bacterial vaginosis
 - Candidiasis
 - Chlamydia infection
 - Gonorrhea infection
 - Syphilis infection
 - Trichomoniasis

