6.3 Accrual, Follow-up, and Sample Size

Each participating study site will target accrual of 240 study participants within the six-month accrual period, with the monthly enrollment targets presented in Section 2.2. Each site also will target retention of 95 percent of enrolled participants annually (or 97.5 percent semi-annually).

As will be described in Section 6.4.2, assessment of the study outcomes related to accrual and retention will not require statistical analysis. However the precision of study estimates of HIV and STD incidence depends on the number of participants enrolled and retained in the study, as well as the "true" seroincidence rate. Shown in Tables 1 and 2 below are the widths of exact 95% confidence intervals around site-specific incidence rates, assuming the accrual schedule presented in Section 2.2 and retention of 97.5 percent of participants semi-annually, with either a sixmonth (Table 1) or twelve-month (Table 2) follow-up period, and an expected 117 and 234 woman-years of follow-up, respectively.

Table 1
95% Exact Confidence Intervals for Infection Rates
Observed in a Six-Month Follow-up Period

Observed in a dix-month i dilow-up i eriod								
No. Infections	Observed	95% Exact						
Observed	Infection Rate	Confidence Interval						
1	1.7%	0.2-6.2%						
2	3.4%	0.9-8.8%						
3	5.1%	1.8-11.2%						
4	6.8%	2.9-13.5%						
5	8.5%	4.0-15.7%						
6	10.3%	5.3-17.9%						

Table 2
95% Exact Confidence Intervals for Infection Rates
Observed in a Twelve-Month Follow-up Period

No. Infections Observed	Observed Infection Rate	95% Exact Confidence Interval
2	1.7%	0.4-4.4%
4	3.4%	1.4-6.7%
6	5.1%	2.6-9.0%
8	6.8%	3.9-11.1%
10	8.5%	5.2-13.2%
12	10.3%	6.5-15.3%

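### Two rules for when a woman's follow-up ends (site calendar date versus 12 months from enrollment) diverge if a site is extended, and the retention endpoint and Table 1 fit neither cleanly

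*Supplement*

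**What the plan says.** **Calendar wording.** Section 2.2 sets the follow-up period at six months or more, "and up to a maximum of 12 months, from the end of the accrual period". It expects HPTN 035 to be activated by six months; failing that, "the follow-up period may be extended for up to another six months, pending activation of HPTN 035". Closure is by site: "On a site-by-site basis, upon activation of HPTN 035, this study will be terminated". The last paragraph of Section 2.2 keeps women who become pregnant or HIV-infected in follow-up until HPTN 035 starts, and Section 4.4 schedules monthly visits across the whole study follow-up period. None of these places gives a stop for the individual woman.

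**Individual wording.** The Schema gives each participant "follow-up for a minimum of six months and a maximum of 12 months". Section 6.1 says: "Each participant will complete a minimum of six and a maximum of 12 scheduled monthly follow-up assessments". Appendix I lists no visit after month 12.

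**Retention.** Section 6.2 lists the endpoint as "Participants retained in the study until the site-specific study end date". Section 6.4.2 divides by all women enrolled at the site. It counts those with a completed scheduled visit in the interval, or known to have died in an earlier one, and compares the result with a 95% annual target.

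**Planned precision.** Section 6.3 bases Tables 1 and 2 on the Section 2.2 accrual schedule and 97.5% semi-annual retention, with an "expected 117 and 234 woman-years of follow-up, respectively". The 2003 letter of amendment corrects the infection counts in both tables. It leaves the woman-years and the follow-up wording unchanged.

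**The concern.** With accrual spread over six months, a calendar end date and a 12-month individual limit give every woman the same follow-up only if the site closes six months after accrual. Section 2.2 allows up to six months more and lists several reasons why that might happen. In an extension, a site must decide whether a woman enrolled in month 1 continues past Month 12. Sections 2.2 and 4.4 suggest that she does; the Schema, Section 6.1 and Appendix I say that she does not. Sites could reasonably act differently.

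Two quantities depend on the answer. One is the woman-years behind the planned intervals. The other is retention, a secondary objective with consequences: under Section 3.5 below-target retention prompts action with the site, and under Section 2.2 performance in this study can delay the move to HPTN 035.

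**Working it through.** **Inputs.** Accrual per site of 20, 30, 40, 50, 50, 50 over months 1 to 6, total 240 (Section 2.2). Retention of 97.5% per six months (Section 6.3). Site closure L = 6 to 12 months after accrual (Section 2.2). Assumptions not in the protocol: enrollment is even within each month, and loss is exponential.

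**1. The plan's own figures.** 240 × 0.5 × 0.975 = 117.0 and 240 × 1.0 × 0.975 = 234.0. With exponential loss, a fixed six or 12 months per woman gives 118.5 and 234.0. So 117 and 234 correspond to every woman having exactly six or exactly 12 months. Neither depends on the accrual schedule. Exact Poisson limits on these totals reproduce the amended tables, apart from some lower limits being truncated and not rounded.

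**2. Mean follow-up without an individual stop.** Average time from enrollment to the end of accrual:

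(20×5.5 + 30×4.5 + 40×3.5 + 50×2.5 + 50×1.5 + 50×0.5) / 240 = 610/240 = 2.54 months.

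Mean planned follow-up is therefore L + 2.54 months. At L = 12 that is 14.54 months (range 12 to 18), or 240 × 14.54/12 = 290.8 woman-years before loss. At L = 6 it is 8.54 months, or 170.8 before loss.

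**3. Woman-years with loss.** With λ = −ln(0.975)/6 per month, a woman planned for T months contributes (1 − e^(−λT))/(12λ) years. T is the time from her enrollment to site closure, limited to 12 months where the stop applies. Percentages are from unrounded totals.

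| Closure, months after accrual | No stop | 12-month stop | Gain from removing stop | Women reaching 12 months before closure (of 240) |
|---|---|---|---|---|
| 6 | 167.7 | 167.7 | 0 | 0 |
| 7 | 186.9 | 186.1 | 0.4% | 20 |
| 8 | 206.1 | 202.6 | 1.8% | 50 |
| 9 | 225.2 | 216.1 | 4.2% | 90 |
| 10 | 244.2 | 226.1 | 8.0% | 140 |
| 11 | 263.1 | 232.0 | 13.4% | 190 |
| 12 | 282.0 | 234.0 | 20.5% | essentially 240 |

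The last column is the cumulative accrual target and ignores dropout. At L = 12 the gain is 16.5% if all enroll at month end (272.6/234.0) and 24.5% if all enroll at month start (291.4/234.0). Expressed the other way, imposing the stop removes 17.0% (234.0/282.0 = 0.830).

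**4. Precision at about 5 per 100 woman-years.** 12 events on 234 gives 5.1% (exact limits 2.6 to 9.0, as in amended Table 2). 14 events on 282 gives 5.0% (2.7 to 8.3).

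**5. Retention if the 12-month stop applies.** On the literal Section 6.2 wording with all enrolled as denominator, a site with no dropout scores at most (240 − 20)/240 = 92% for a one-month extension. For two to six months the ceilings are 79%, 62%, 42%, 21% and about 0%. If the Section 6.4.2 intervals run in participant time, a woman who completes Month 12 is retained and no such ceiling arises. If they are calendar quarters of the site period, it does.

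**6. Table 1.** Closure six months after accrual gives each woman six to 12 months under either rule: 167.7 woman-years, against 117 in Section 6.3 (167.7/117 = 1.43, or 43% more).

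**The case against.** The two sets of passages can be read together: the site stays open six to 12 months after accrual, and each woman contributes six to 12 months within that window. Section 6.1 itself puts the 12-visit maximum beside a total study length of 12 to 18 months. Section 2.2 refers to the Schema and Appendix I for the design and visit schedule, and the Section 3.2 travel, relocation and pregnancy-plan criteria look 12 months ahead. No passage states 18 months for one woman; that is inferred from Section 2.2. All of this stands. But Section 2.2 does not state the joint reading, and Section 4.4 and the paragraph on pregnant and HIV-infected women pull the other way. The joint reading is also the one under which the Section 6.2 endpoint goes wrong.

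It is also fair to say that 20.5% is the extreme. At the expected closure the difference is zero, and with a three-month extension it is about 4%.

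Three stronger inferences are tempting, and the documents do not support them:

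- **That a site with perfect retention must miss the 95% target.** This holds only on the literal Section 6.2 wording or with calendar intervals. Section 6.4.2 requires a completed scheduled visit in the interval, and those visits fall on enrollment anniversaries (Section 4.4).
- **That Table 2 proves the 12-month limit.** Its 234 is a flat product that ignores staggered accrual. The 117 in Table 1 is built the same way and fits neither rule.
- **That the primary result is biased.** Section 6.4.1 divides confirmed seroconversions by woman-years of follow-up, so neither stop rule biases the rate in itself.

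**Conclusion.** The follow-up passages conflict in the current text and must be reconciled. The documents do not settle which rule is intended. The effect on woman-years ranges from nothing at the expected six-month closure to about 20% at the longest extension (16.5% to 24.5% by enrollment timing within the month), given the accrual and retention targets and exponential loss. The interval for the primary rate changes little even then. The practical consequences are whether visits continue past Month 12, for which Appendix I has no schedule, and how retention is scored. On retention the defect is an undefined interval and an endpoint label that can contradict the individual limit; failure of the target is not inevitable.

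Separately, Table 1 understates woman-years for the scenario that the protocol expects, about 168 against 117 per site. Choosing a stop rule does not mend that.

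**What to change.** State one stop rule and use it in the Schema, Section 2.2 (including the paragraph on pregnant and HIV-infected women), Section 4.4, Section 6.1 and Appendix I. The choice is the sponsor's.

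- **If the 12-month limit is kept:** say in Sections 2.2 and 4.4 that a woman's follow-up ends at the earlier of Month 12 and the site end date. Define the Section 6.2 retention endpoint and the Section 6.4.2 intervals in participant time, to the same point. The 234 woman-years in Table 2 then stand for a full 12-month period. This is wording only, with no added visits or participants.
- **If it is not kept:** amend the Schema and Section 6.1, extend the Appendix I schedule past month 12, and restate Table 2 for about 282 woman-years. The cost is the extra visits and tests during an extension.

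In either case restate Table 1 for about 168 woman-years per site, with the enrollment-timing and loss assumptions given. That costs a recalculation only.
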